# 6.3 Method of Minimizing or Avoiding Bias

If efficacy is confirmed in the 100 mg group and there are no safety concerns, in the next step patients in each group (the CDI group and the enteric infection group) will be randomized to the 200 mg and 50 mg groups by stratified allocation using country (Japan, Korea, or Singapore) as the stratifying variable.

# 7 Trial Procedures

# 7.1 Schedule and Procedures

The investigator or subinvestigator will perform observations, examinations, and evaluations in accordance with Table 7-1, Schedule of Observations, Examinations, and Evaluations.

Table 7-1 Schedule of Observations, Examinations, and Evaluations

		Screening	Administration period		End of administration	FU1	FU2	Withdrawal	
Observation	CDI group	-	1	4	10	11	24	38	-
day	Enteric infection group	-	1	4	7	8	14	-	-
Allowance	CDI group	-2	0	+1	0	+1	±3	±3	+2
range	Enteric infection group		Ů		Ů				. 2
	nformed consent	X							
Inclusion/Exclu		X							
Patient backgro		X							
Height/Body w	eight	X							
Toxin A/B scre	eening, PCR test, or colonoscopy a	X							
Clinical laboratory test (hematological test, biochemical test, urinalysis) a		X							
Pregnant test b		X							
IMP									
Assignment			X						
Administration			X	X	X				
Confirmation of	f compliance			X		X			
Safety assessment									
Physical examination		X		X		X	X	X	
Clinical laboratory test		Х		X		X	X	X	X
(hematological test, biochemical test, urinalysis)		Λ		21		Λ	71	71	A
Vital signs		X		X		X	X	X	X
(blood pressure, pulse rate, body temperature)		Λ		Λ		Λ	Λ	Λ	
12-lead ECG		X		X		X			X d
Adverse events		$\leftarrow$							$\longrightarrow$
Concurrent dru	gs and combination therapies	$\leftarrow$							$\longrightarrow$
	sment of CDI group								
Bacterial cultur	re test	X		X		X		X	X
Toxin A/B test		X		X		X		X	X
	of isolated strain	X				X		X	
Clinical respons	se			X		X			X d
Recurrence of CDI								X	X c
Confirmation of patient's clinical symptom		X		X		X	X	X	X
Patient diary			$\leftarrow$						$\rightarrow$
Efficacy assessment of enteric infection group									
Bacterial culture test		X		X		X			X d
Drug sensitivity of isolated strain		X				X			
Clinical response				X		X			X d
Confirmation of patient's clinical symptom		X		X		X	X		X
Patient diary			$\leftarrow$				<del></del>		>
Pharmacokinet	ics assessment								
Plasma drug co	Plasma drug concentration			X e					
0									

<sup>a To be performed at the trial site to confirm the eligibility, separately from the test for efficacy and safety assessment. Colonoscopy will be performed when necessary only in the CDI group.

b Pregnancy test will be performed only in women with childbearing potential

Outpatient: once within 12 hours after morning administration but before evening administration

## 7.1.1 Acquisition of Informed Consent

The investigator or subinvestigator will obtain written consent directly from patients before any screening examinations can take place. After obtaining informed consent, the investigator, subinvestigator, or a trial associate will register each patient in either the IVRS or the IWRS to assign a patient number. The patient number (three-digit trial site number + S + five-digit sequential serial number at the trial site) and the date of written informed consent will be recorded on the source documents and CRF. The investigator or subinvestigator will confirm the content of enrollment, and perform screening examination.

# 7.1.2 Screening Examination: Allowance – 2 Days

The investigator or subinvestigator will perform the following screening examinations, and select patients who meet the inclusion criteria and do not fall under any of the exclusion criteria.

Virus quick test, toxin A/B assay, PCR, colonoscopy, and clinical laboratory tests (hematology test, biochemistry test, and urinalysis) will be performed by the method specified by the trial site. Eligibility will be assessed based on the test result at the trial site. The latest data from colonoscopy performed within 48 hours before administration of IMP can be used for screening, even if they are obtained before informed consent.

For bacterial culture test, toxin A/B assay, PCR, and drug sensitivity test on isolated strains at screening, stool specimens will be collected within 48 hours before the administration of IMP (The latest data performed within 48 hours for CDI group or 24 hours for Enteric infection group before administration of IMP can be used for screening, even if they are obtained before informed consent). Stool specimens and specimens for clinical laboratory tests collected at the screening examination will also be tested by the laboratory for microbiological examination (hereafter, microbiological laboratory), and the central laboratory for clinical laboratory tests (hereafter, central laboratory).

- Height, body weight
- Confirmation of patients' clinical symptoms (daily stool count, stool symptoms, bloody stool, fever, abdominal pain, nausea, and vomiting)

<sup>c To be performed only in the case of withdrawal after the end of administration.

d To be performed only in the case of withdrawal during administration period.

Inpatient: 1 (± 15 minutes), 2 (± 15 minutes), and 4 hours (± 30 minutes) after morning administration.

- Virus quick test (if considered necessary by the investigator or subinvestigator)\*
- Toxin A/B assay\*
- PCR or colonoscopy: CDI group only\*
- Collection of stool specimens (the following items will be tested by the microbiological laboratory)
  - Bacterial culture test
  - Toxin A/B assay: CDI group only
  - Drug sensitivity test on isolated strains
- Physical examination
- Clinical laboratory tests (hematology test, biochemistry test, and urinalysis)\*
- hCG pregnancy test

The pregnancy test will be performed for female patients at the trial site. A pregnancy test will not be required for patients who have undergone bilateral oophorectomy or hysterectomy, or have not experienced menses for at least 12 consecutive months for whatever other medical reasons.

- Vital signs (blood pressure, pulse rate, and body temperature)
- 12-lead ECG
- Confirmation of concomitant drugs and therapies
   \*Use the test result at the trial site to assess eligibility at the time of screening.

#### 7.1.3 Patient Information

At the time of obtaining informed consent or at the screening examination, the investigator or subinvestigator will check and record the following patient information in the source documents and CRF.

- Disease group (CDI group, enteric infection group)
- Date of informed consent acquisition
- Patient number
- Patient background (sex, date of birth, country where the trial will be conducted, race)
- Inpatient/outpatient (at the time of informed consent)
- Medical history and concomitant disease
- Clinical condition of patients (daily stool count, fecal properties, bloody stool, fever, abdominal pain, nausea, and vomiting)
- Diagnostic procedures of CDI (toxin A/B test, PCR, colonoscopy): CDI group only
- History of CDI: CDI group only
- Number of CDI episodes and date of the latest diagnosis of CDI if there is a history of CDI

## 7.1.4 Allocation of Patients to Dosing Groups

The investigator or subinvestigator will verify that the patient meets the inclusion criteria and does not fall under any of the exclusion criteria based on the results of the screening examination, and register the information of patients in either the IVRS or the IWRS. The investigator or subinvestigator will obtain the allocated dosage information of IMPs from IVRS or IWRS and administer the allocated dose of IMPs to patients. The investigator or subinvestigator will record the information on the following dose group to the source documents and CRF.

• Dosage groups (50 mg group, 100 mg group, 200 mg group, and 400 mg group)

# 7.1.5 Examination and Evaluation for *Clostridium Difficile* Infection Group

Collect stool specimens to be used for bacterial culture test, toxin A/B assay, and drug sensitivity test on isolated strains within 24 hours before each test.

# 7.1.5.1 Day 1

- Confirmation of adverse events
- Confirmation of concomitant drugs and therapies

# 7.1.5.2 Day 4: Allowance + 1 Day

- Collection of stool specimens (the following items will be tested by the microbiological laboratory)
  - Bacterial culture test
  - Toxin A/B assay
- Confirmation of IMP compliance
- Confirmation of patients' clinical symptoms on Days 1 to 3 (daily stool count, stool symptoms, bloody stool, fever, abdominal pain, nausea, and vomiting)
- Assessment of clinical response
- Clinical laboratory tests (hematology test, biochemistry test, and urinalysis)
- Blood sampling for measuring plasma concentration
  - Inpatient: 1 (± 15 minutes), 2 (± 15 minutes), and 4 hours (± 30 minutes) after morning administration
  - Outpatient: once within 12 hours after morning administration but before evening administration.
- 12-lead ECG
- Vital signs (blood pressure, pulse rate, and body temperature)

- Physical examination
- Confirmation of adverse events
- Confirmation of concomitant drugs and therapies

# 7.1.5.3 Day 11 (End of Treatment): Allowance + 1 Day

- Collection of stool specimens (the following items will be tested by the microbiological laboratory)
  - Bacterial culture test
  - Toxin A/B assay
  - Drug sensitivity test on isolated strains
- Confirmation of IMP compliance
- Confirmation of patients' clinical symptoms on Days 4 to 10 (daily stool count, stool symptoms, bloody stool, fever, abdominal pain, nausea, and vomiting)
- Assessment of clinical response
- Clinical laboratory tests (hematology test, biochemistry test, and urinalysis)
- 12-lead ECG
- Vital signs (blood pressure, pulse rate, and body temperature)
- Physical examination
- Confirmation of adverse events
- Confirmation of concomitant drugs and therapies

## 7.1.5.4 Day 24 (at Follow-up 1): Allowance ± 3 Days

- Confirmation of patients' clinical symptoms on Days 11 to 23 (daily stool count, stool symptoms, bloody stool, fever, abdominal pain, nausea, and vomiting)
- Clinical laboratory tests (hematology test, biochemistry test, and urinalysis)
- Vital signs (blood pressure, pulse rate, and body temperature)
- Physical examination
- Confirmation of adverse events
- Confirmation of concomitant drugs and therapies

## 7.1.5.5 Day 38 (at Follow-up 2): Allowance ± 3 Days

- Collection of stool specimens (the following items will be tested by the microbiological laboratory)
  - Bacterial culture test
  - Toxin A/B assay
  - Drug sensitivity test on isolated strains

- Confirmation of patients' clinical symptoms on Days 24 to 37 (daily stool count, stool symptoms, bloody stool, fever, abdominal pain, nausea, and vomiting)
- Assessment of recurrence of CDI
- Clinical laboratory tests (hematology test, biochemistry test, and urinalysis)
- Vital signs (blood pressure, pulse rate, and body temperature)
- Physical examination
- Confirmation of adverse events
- Confirmation of concomitant drugs and therapies

## 7.1.6 Examination and Evaluation for Enteric Infection Group

Collect stool specimens for bacterial culture test and drug sensitivity test on isolated strains within 24 hours before each test.

## 7.1.6.1 Day 1

- Confirmation of adverse events
- Confirmation of concomitant drugs and therapies

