# 3.3.2 Efficacy Endpoints

# 3.3.2.1 Microbiological Outcome

Microbiological outcome will be judged according to the assessment criteria shown in Table 3.3-1 and Table 3.3-2 for the bacterial strain isolated as the causative pathogen based on the data from the microbiological examination. For infection due to multiple causative pathogens, microbiological outcome will be assessed for each individual pathogen.

 Table 3.3-1
 Assessment Table for Microbiological Outcome

	Assessment of				
Baseline	Day 4	End of Treatment	Microbiological Outcome		
+	-	_	Excellent		
+	1				
_	+	_	Good		
+	Not applicable				
+	1				
_	+	,	Poor		
+	_	+			
+	Not applicable				
	Others		Unknown/ indeterminate		

+: culture positive, -: culture negative

Not applicable: Bacterial culture test was not performed. The causative pathogen was not isolated or identified.

Table 3.3-2 Assessment Criteria for Microbiological Outcome

Assessment of Microbiological Outcome	Definition			
Excellent	Pathogen is absent from bacterial culture obtained at Day 4 and at the end of treatment.			
Good	Pathogen is still present in bacterial culture obtained at Day 4, and absent from bacterial culture at the end of treatment.			
Poor	Pathogen is still present in bacterial culture obtained at the end of treatment.			
Unknown/indeterminate	Applicable to none of the above but falls under the cases below for example.     Cultures are not available because of withdrawal from the study or other reasons.			
	Culture was obtained after the use of prohibited concomitant drugs/therapies.			
	Any other circumstance, which makes it impossible to define the microbiological response.			

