# 3.3.2.3 Clinical Response

The investigator or subinvestigator will refer to the information from patients (eg, patient diary), and assess clinical response at the time of observation (Day 4 and end of treatment) according to the assessment criteria shown in Table 3.3-3.

Table 3.3-3 Assessment Criteria for Clinical Response

Clinical Response Assessment	Definition
Clinical cure	Meeting all the following criteria within 24 hours before observation  No liquid or unformed stool
	No abdominal symptoms and no other symptoms (fever, nausea, vomiting)
	No need of medication or therapy to treat CDI or enteric infection
Clinical improvement	Fulfilling at least one of the following criteria within 24 hours before observation  • Liquid or unformed stools ≤ 2 times/day
	No abdominal symptoms and no other symptoms (fever, nausea, vomiting)
	No need of medication or therapy to treat CDI or enteric infection
Clinical failure	Fulfilling none of the above-mentioned clinical improvement criteria.  Patients who received medication or therapy to treat CDI or enteric infection prior to the time of observation are to be assessed as "clinical failure".

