# 7.1.6.3 Day 8 (End of Treatment): Allowance + 1 Day

- Collection of stool specimens (the following items will be tested by the microbiological laboratory)
  - Bacterial culture test
  - Drug sensitivity test on isolated strains
- Confirmation of IMP compliance
- Confirmation of patients' clinical symptoms on Days 4 to 7 (daily stool count, stool symptoms, bloody stool, fever, abdominal pain, nausea, and vomiting)
- Assessment of clinical response
- Clinical laboratory tests (hematology test, biochemistry test, and urinalysis)
- 12-lead ECG
- Vital signs (blood pressure, pulse rate, and body temperature)
- Physical examination
- Confirmation of adverse events
- Confirmation of concomitant drugs and therapies

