#### 2) Method of Examination

Collect approximately 3 g of stool from the patient using the stool sample container provided by the microbiological laboratory. The containers will be labeled with the study number, patient number, and sampling day. Collect stool specimens within 48 hours prior to IMP administration for the screening time point and within 24 hours before the observation day for other time points. Store stool samples at approximately 4°C until a designated courier collects them.

The microbiological laboratory will follow the predetermined procedures and perform the culture and identification by centralized measurement. The isolated strains will be stored in order to enable exploratory investigation in the future on the bacteriological and genetic characteristics other than drug sensitivity of the isolated strains.

If the result of measurement requires notification in line with the Infectious Diseases Control Law, each trial site will submit notification in accordance with relevant laws, regulations, and notifications of each country.

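### A patient whose diarrhea has resolved and who passes no stool in the 24-hour sampling window is lost from the microbiological analysis; failures can be lost too, so the direction of bias is unknown

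*Protocol*

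**What the plan says.** **Sampling window.** Section 7.1.6 (enteric infection group): "Collect stool specimens for bacterial culture test and drug sensitivity test on isolated strains within 24 hours before each test". Section 7.1.5 (CDI group) has the same rule and adds the toxin assay; its window reads "drug sensitivity test on isolated strains within 24 hours before each test". Section 7.2.2.1, Method of Examination, anchors the window to the visit instead: "within 24 hours before the observation day for other time points". The end-of-treatment visit may slip by one day in both groups; for enteric infection the heading reads "7.1.6.3 Day 8 (End of Treatment): Allowance + 1 Day".

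**Clinical cure.** The first criterion in Table 3.3-3, over the 24 hours before observation, is "No liquid or unformed stool". A patient who passes no stool at all meets it.

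**No culture.** Among the Unknown/indeterminate cases, Table 3.3-2 lists "Cultures are not available because of withdrawal from the study or other reasons" and also "Culture was obtained after the use of prohibited concomitant drugs/therapies". There is no presumed-eradicated category.

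**Consequences.** Unknown/indeterminate patients are left out of the assessable count (3.4), the MPPS (11.1.3) and the elimination rate (11.3.4.1). The toxin-positive rate is computed in the MPPS, over patients assessed for microbiological outcome (11.3.4.2). Missing data are not imputed (11.2). Shortfalls in assessable patients are made up by enrolling more (3.4, 11.5). The CPPS requires every scheduled examination up to end of treatment or withdrawal (11.1.4).

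**The concern.** Diarrheal patients produce specimens easily; patients who have recovered may not. A patient who meets the stool criterion for cure by passing nothing in 24 hours cannot supply a culture for those same hours. The sampling rule thus makes the existence of the endpoint depend on how the patient is doing, and the analysis drops those with no result. Read literally, the missed culture also removes the patient from the CPPS, and so from the analyses of clinical response, recurrence, time to resolution and symptoms.

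At stake are the elimination and toxin-positive rates in arms of about 10 (CDI) or 5 (enteric) assessable patients, where one loss is visible. The DRC's view of efficacy at 100 mg decides which doses follow (3.1), although the protocol does not say how it weighs culture results. Top-up enrolment restores the count but not the mix of patients. It also exposes extra patients, although Section 11.5 aims to keep exposure to a minimum.

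**Working it through.** **1. The plan's own figure.** Section 11.5 assumes detection of almost 100% in CDI and 50% in enteric infection. Expected assessable per dose: 10 × 1.0 = 10 and 10 × 0.5 = 5, which reproduces the targets. The enteric 5 is only an expected value: P(at least 5 of 10 at 50%) = 62.3%. If a share of culture-positive enteric patients (assumed) also lacks a usable end-of-treatment culture:

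| Loss | Expected assessable | P(at least 5 of 10) |
|---|---|---|
| 10% | 10 × 0.5 × 0.9 = 4.5 | 49.6% |
| 20% | 10 × 0.5 × 0.8 = 4.0 | 36.7% |
| 30% | 10 × 0.5 × 0.7 = 3.5 | 24.9% |

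**2. How often no stool might occur.** The documents give no figure. Assume a Poisson process at 0.7, 1.0 or 1.5 stools per day after resolution, so P(no stool) = exp(−rate × days):

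| Period covered | 0.7/day | 1.0/day | 1.5/day |
|---|---|---|---|
| 24 hours | 50% | 37% | 22% |
| 48 hours (+1 day allowance fully used) | 25% | 14% | 5% |
| 72 hours (24 before and 48 after the visit) | exp(−2.1) = 12% | exp(−3.0) = 5% | exp(−4.5) = 1% |

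More regular habits make all of these smaller.

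**3. Effect on the elimination rate.** Let p be the true rate, m the share of eradicated patients without a usable culture, and f the same share among non-eradicated patients. Then

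observed rate = p(1 − m) / [p(1 − m) + (1 − p)(1 − f)].

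The documents give none of p, m or f. With p = 0.80 assumed:

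| m | f | Observed |
|---|---|---|
| 10% | 0 | 0.72/0.92 = 78.3% |
| 20% | 0 | 0.64/0.84 = 76.2% |
| 30% | 0 | 0.56/0.76 = 73.7% |
| 10% | 10% | 0.72/0.90 = 80.0% |
| 10% | 30% | 0.72/0.86 = 83.7% |
| 10% | 50% | 0.72/0.82 = 87.8% |

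The bias is downward when m > f, zero when m = f and upward when m < f.

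**4. One patient at the planned size** (one strain per patient, before any top-up). Losing one eradicated patient moves 4/5 (80%) to 3/4 (75%), or 8/10 (80%) to 7/9 (77.8%). Losing one failing patient moves 8/10 to 8/9 (88.9%). Counting the lost patient both ways brackets the truth: for 7/9 observed among 10 treated, 7/10 = 70% to 8/10 = 80%; for 8/9 observed, 8/10 = 80% to 9/10 = 90%.

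**5. Can failures be lost?** Yes. Section 9.2 withdraws a patient when other CDI or enteric infection therapy is used or judged necessary (item 3), or when worsening makes continuation inappropriate (item 6). Table 3.3-2 voids a culture taken after prohibited therapy. Section 7.1.7 lets withdrawal examinations be omitted on refusal or in an emergency. So f is not zero by design.

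**The case against.** A reader might infer that failing patients always stay in, so that the elimination rate is biased downward, most of all at the best dose. The documents do not support this. Failures leave through the routes in step 5 of the working, and clinical cure is not bacterial elimination: a patient who passes no stool may still carry the pathogen. This objection stands in full.

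The rule is also milder than it first looks. The visit can move by a day, and Table 3.3-1 still scores patients whose Day 4 culture is missing, so only the end-of-treatment specimen is critical. This stands, and reduces the loss without removing it.

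No section voids a stool collected late. It would be a deviation, and its use could be settled in the SAP or under Section 11.2, which leaves problem data to the sponsor. This stands only in part: an analysis rule can decide how to use a specimen that exists, but the protocol asks nobody to collect one.

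Finally, the trial is descriptive, its size was not set by statistical methods, and the intervals are very wide: exact 95% intervals are 28.4% to 99.5% for 4/5 and 44.4% to 97.5% for 8/10. A shift of a few points is small beside that. True, but the loss is avoidable, it costs scarce assessable patients, and the interval does not show it.

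**Conclusion.** The concern holds in limited form. A stated rule, and not merely absent detail, makes the end-of-treatment culture depend on outcome, in both disease groups. Patients without one leave the microbiological analyses without imputation and, read literally, the CPPS as well. The three statements of the window also do not agree: two run back from the test and one from the observation day, and the latter could even be read to exclude a stool passed on the visit day.

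Neither the direction nor the size of the net bias can be established. Under the assumptions in the working, a true 80% could read anywhere from 73.7% to 87.8%. The no-stool figures rest wholly on the assumed stool rates and Poisson model. What is firm is that each loss takes one patient from an arm of about 5 or 10, and that in the enteric group the target is already missed in 37.7% (100% − 62.3%) of cases at 10 enrolled under the plan's own detection rate. The change is worth making, but it does not undermine the trial.

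**What to change.** 1. Reconcile the window in Sections 7.1.5, 7.1.6 and 7.2.2.1 to one anchor, and say whether a stool passed on the visit day counts.
2. For end of treatment only, if no stool is available in the window, collect the first stool passed within a short fixed period after the visit, for example up to 48 hours, using a take-home container. Count it only if no other antibacterial and no CDI or enteric infection therapy was taken in between. The condition matters in CDI, where the restriction on other antibacterials ends on the day of the end-of-treatment examination (6.2.2).
3. List the sampling dates of late specimens (the CRF already records them) and report the elimination and toxin-positive rates with and without these specimens.
4. Add a sensitivity analysis over all treated, baseline culture-positive patients, giving the elimination rate with those lacking a usable end-of-treatment culture counted first all as eliminated, then all as not eliminated. This also covers failures lost to other therapy or withdrawal.
5. State whether an absent stool counts as a missed examination for the CPPS.

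The period should stay short. In the enteric group, 48 hours after a visit on Day 8 + 1 reaches Day 11, the first day of the FU1 window (Day 14 ± 3); 72 hours would reach Day 12. No culture is scheduled at FU1 in that group, so none is displaced.

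Cost: a sampling amendment, containers, cold storage until some later courier pick-ups, and a few extra output lines. The downside is that a few specimens are taken one to two days after the visit, further off drug than the rest, which is why the rates are shown both ways.
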